## 1 PROTOCOL SYNOPSIS

Sponsor:	Advanced Cooling Therapy d/b/a Attune Medical, [name]
Version:	1.0
Protocol ID	201904751
PI/Site:	
Objective:	This pilot study will evaluate the efficiency impact of conducting active temperature management during cardiac ablation procedures.
Patient Population:	This study is intended for patients undergoing left atrial ablation including pulmonary vein isolation for the treatment of atrial fibrillation.
Study Design:	Prospective, single center pilot study
Study Conduct:	
This prospective interventional pilot study will use the FDA cleared Attune Medical esophageal heat transfer device (ensoETM) to actively cool the esophagus when RF ablations are performed on the posterior atrial wall and to actively warm the patient at all other times to minimize perioperative hypothermia.
 
In consented participants, following induction of anesthesia and intubation, the ensoETM will be placed into the esophagus according to the device Instructions and maintained at 40-42°C. Active cooling will be initiated approximately 15 minutes prior to any ablations placed on the posterior left atrium. The ensoETM will continuously circulate 4-6°C water inside the device during all ablations directed at the posterior wall of the atrium. Once all ablations to the posterior wall of the atrium are complete, the water set-point will be returned to nominal until the conclusion of the procedure. Total procedure time from trans-septal puncture to pulmonary vein isolation (PVI) will be recorded.
 
All patients will be followed up in total for 6 weeks (Long Term FU visit) after the procedure to document any clinical complication related to thermal esophageal injuries if applicable.

Study Duration:	The study duration is projected to be approximately 145 days (estimated 3-month enrollment and a 6-week long term follow-up window).
Inclusion Criteria:	

1. Adult patients (age over 18 years)

---

- 2. Undergoing first left atrial ablation for the treatment of atrial fibrillation including pulmonary vein isolation
- 3. Undergoing catheter-based ablation procedure using radiofrequency energy
- 4. Patients must be able to understand and critically review the informed consent form.
- 5. Subjects must understand and agree to study requirements and sign a written informed consent

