## **6 STUDY PROCEDURE AND ASSESSMENTS**

*Table 2: Schedule of Assessments and Procedures*

Assessment/ Evaluation	Baseline (-14 days)	Day 0 (pre-admission)	Index Procedure	Discharge (+1d)
Pre-screening for Inclusion/ Exclusion Criteria	X			

Medical History	X			
Demographics	X			
Informed Consent		X		
Randomization	N/A			
Device-related Adverse Events			X	X

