### 6.4 Hospital Discharge

---

Patients discharged from the hospital following the procedure will follow post procedural standard of care for AF Ablation procedures.

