## 6.5 Study Duration and Early Termination

Study duration is expected to be minimum of 3 months. The IRB may suspend or prematurely terminate the clinical study at the investigation site. If suspension or premature termination occurs, the terminating party shall justify its decision in writing and promptly inform the other parties involved. If, for any reason, the Sponsor suspends or prematurely terminates the investigation the Sponsor shall inform the responsible regulatory authority and Ethics Committee as appropriate.

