## 6.7 Adverse Event (AE) Reporting Requirements

All ADEs will be documented according to institutional standards. All ADEs must be monitored until they are adequately resolved or explained.

SAEs where causal relationship to device and procedure can be excluded will be added to a summary table and reported quarterly. At the end of the study an evaluation report of all SAEs will be provided to the Ethics Committee if required.

Definitions regarding adverse events can be found in Section 9.

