## 8.3 DURATION OF FOLLOW-UP POST ADVERSE EVENTS

All adverse events related to the device procedure (ADE) must be followed until resolution or until stable clinical endpoint is reached. All required treatments and outcomes of the adverse events must be recorded per reporting requirements defined in Section 5.

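### The six-week follow-up for esophageal injury promised in the synopsis is not in the visit schedule, and the adverse-event recording rule conflicts with the safety tables planned from it

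*Combined protocol and SAP*

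**What the plan says.** **Follow-up.** The synopsis (Study Conduct) says "All patients will be followed up in total for 6 weeks (Long Term FU visit) after the procedure to document any clinical complication". The purpose is to capture "any clinical complication related to thermal esophageal injuries if applicable", with no limit on what caused the injury. The synopsis entry on duration counts the window: "The study duration is projected to be approximately 145 days (estimated 3-month enrollment and a 6-week long term follow-up window".

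Table 2 in Section 6 has four columns: baseline, day 0, index procedure and discharge (+1d). Its only safety row, "Device-related Adverse Events", is marked at the last two. Section 6.4 says that discharged patients "will follow post procedural standard of care for AF Ablation procedures". Section 6.5 says "Study duration is expected to be minimum of 3 months" and mentions no follow-up window. Two other passages look beyond discharge. Section 6.7 says "All ADEs must be monitored until they are adequately resolved or explained", and Section 8.3 says that adverse events related to the device procedure "must be followed until resolution or until stable clinical endpoint is reached".

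**Recording.** Section 5.4.4.3 plans incidence summaries for every adverse event and, as a separate category, for device-related ones. Its last sentence then rules out recording any event that is not specifically device-related. Section 6.7 asks for a quarterly table of serious events judged unrelated to both device and procedure, and for a final report on all serious events if the Ethics Committee requires it. Section 8.1 defines an adverse event without reference to the device.

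**Safety population.** Section 5.4.4.2 limits it to enrolled subjects who underwent ablation, and Section 5.4.4.3 runs every safety analysis on it. Section 4.1 has the device placed after intubation, before any ablation.

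**The concern.** Site staff work from the schedule and the procedures section. Anyone following Table 2 and Section 6 would make no study contact after discharge, and the follow-up promised for all patients could be omitted without a deviation being noticed.

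Holding the visit would not be enough. Section 3.1 attributes esophageal injury to the radiofrequency energy. An injury attributed in that way is what the visit exists to document, but the last sentence of Section 5.4.4.3 could keep it out of the database. Two people classifying the same event could each point to a passage in support.

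What is at stake is the completeness of the safety results. The primary endpoint, time from trans-septal puncture to pulmonary vein isolation, does not depend on any of this.

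**Working it through.** **1. Does the stated duration include the six-week window?** Inputs: 3 months of enrollment (90 to 92 days), 6 weeks × 7 = 42 days (both from the synopsis), and the 14-day baseline window of Table 2. Adding the baseline window is an assumption.

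| Components | Days |
|---|---|
| Enrollment + 42 | 132 to 134 |
| Enrollment + 42 + 14 | 146 to 148 |
| Enrollment + 1 (Table 2 only) | 91 to 93 |
| Enrollment + 1 + 14 | 105 to 107 |

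The stated figure of about 145 days is reproduced to within 3 days once the baseline window is added. Without the six-week window the total is at most 107 days, so the synopsis figure does rely on the follow-up. The three-month minimum in Section 6.5 omits the window, but a minimum does not conflict numerically with 145.

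**2. How much of the promised follow-up is scheduled?** Table 2 marks adverse events in 2 of its 4 columns, the later being discharge (+1d).

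- Discharge on day 1 (assumption): 42 − 1 = 41 days unscheduled; 41/42 = 97.6%.
- Discharge on day 2: 40/42 = 95.2%.
- Discharge on day 3: 39/42 = 92.9%.

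Sections 6.7 and 8.3 do not close the gap. They follow events already identified and set no contact at which a new one would be found.

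**3. Was the visit lost or removed?** The contents list nine entries under Section 6 (6.1 to 6.9). The body has seven, numbered continuously from 6.1 to 6.7. The two without a body section are Post-ablation Endoscopy and Long Term Follow-Up. Six contents entries show a bookmark error (5.4.4, 6.4, 6.6, 7, 7.1 and 7.2), and none of those headings has a body section. Section 6.7 also sends the reader to Section 9 for definitions that now stand in Section 8. This fits deliberate removal at least as well as accidental loss. The documents do not say which, so the synopsis may be the outdated text.

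**4. Can the recording rule and the planned tables both be followed?** If only device-related events are recorded:

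- The summary of every adverse event and the summary of device-related events in Section 5.4.4.3 contain the same events. Because the section lists them as separate categories, the first cannot be shorthand for the second.
- The table of unrelated serious events in Section 6.7 has no study-recorded entries.
- Section 5.4.1, which has adverse events entered on forms without a relatedness limit, is in tension with the rule but does not contradict it outright.

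**5. Would a thermal esophageal injury be recorded?** Under the synopsis, yes, whatever its cause. Under the last sentence of Section 5.4.4.3, possibly not. The broad definition of a device event in Section 8.1, and the inclusion of device-related procedures in Section 5.4.4.3, could be read to cover it. Non-recording is therefore possible, not certain.

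**6. Who is left out of the safety tables?** A patient injured at insertion whose ablation is then cancelled has been exposed to the device and would have the event documented, but falls outside the safety population and so outside every safety table.

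**The case against.** The strongest reply is that this is a stale synopsis. If the visit was deliberately removed, Table 2 and Sections 6.4 and 6.5 agree with one another, and only a few synopsis sentences need cleaning up. That possibility stands. But the synopsis is part of the current plan, one of the two texts is wrong, and the sponsor must say which.

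A second reply is that the 98% overstates the gap, since a single visit on day 42 would leave most days without contact. But such a visit would ask about the whole interval, so the count does describe the period left unascertained. It is not a count of missed events. The documents give no rate for late complications, and what standard care after discharge involves is not described.

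Third, Section 6.7 could be a reporting duty lying outside the study's own recording. The text does not say so, and that reading leaves the conflict within Section 5.4.4.3 untouched.

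Fourth, the intended scope looks device-related throughout, and dropping the summary of every adverse event would be the simpler repair. That would make Section 5.4.4.3 agree with itself. It would still leave the synopsis's purpose and the Section 6.7 table without data behind them.

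Finally, insertion injuries are recorded under Section 5.4.4.3 in any case, and no frequency is given for cancelled ablations. Both are true, which is why that part is secondary. Recording an event does not bring it into the tables.

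**Conclusion.** The concern holds and should be fixed. The synopsis commits to a six-week contact that the schedule does not contain, leaving 41 of 42 days (98%) without scheduled ascertainment if discharge is on day 1, or 93% to 95% if it is on day 3 or 2, for every one of up to 20 patients. The recording rule cannot be followed together with the summary of every adverse event in the same section, and as written it would leave the Section 6.7 table empty of study-recorded events. The safety population can exclude a patient exposed to the device.

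That the passages disagree is certain. How many events would be missed cannot be estimated, because the documents give no rates for late complications or for ablations cancelled after device placement. The effect is confined to safety ascertainment.

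**What to change.** 1. **Visit.** Decide whether the six-week contact is part of the study. If it is, add it to Table 2, Section 6 and the duration in Section 6.5, with adverse-event ascertainment at that contact. If it was removed on purpose, amend the synopsis text and the 145-day duration, and state that events after discharge are not systematically captured. In either case, bring the contents into line with the body.
2. **Recording rule.** Amend the last sentence of Section 5.4.4.3 so that serious adverse events and clinical complications of thermal esophageal injury are recorded whatever the attribution, with device relatedness as a recorded field. Align the planned summary of every adverse event and Section 6.7 with that rule. Arrhythmia recurrence can stay out of scope.
3. **Safety population.** Define it as all subjects in whom insertion of the device was attempted.

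The cost is wording and table edits, plus a few more events to record and classify in up to 20 patients. Keeping the visit adds nothing beyond what the synopsis already promises.

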**Exclusion Criteria:**

- 1. Patients who are unable to provide informed consent.
- 2. History of prior AF ablation procedures with ablation in the left atrium.
- 3. Significant co-morbidities that preclude standard ablation procedure.
- 4. Patients with <40 kg of body mass
- 5. Patients with relevant esophageal pathology (e.g. esophageal cancer, esophageal varices)

**Primary Endpoint:**

Total time of active ablation procedure, measured from trans-septal puncture to achievement of PVI.

**Sample Size:**

Up to 20 participants will be enrolled in the study.

### 3 INTRODUCTION

#### 3.1 Background

Left atrial catheter ablation including pulmonary vein isolation is a standard therapy in the management of symptomatic atrial fibrillation; however thermal esophageal injury is a known potential consequence of this procedure. Delivery of radiofrequency (RF) energy necessary to perform left atrial ablation has the potential to cause injury to the nearby esophagus including ulceration, hematoma, spasm, esophageal motility disorders, and, in the most extreme case, atrial-esophageal fistula. Esophageal mucosal lesions are the likely precursor to AEF, and esophageal mucosal lesions have been detected on post-ablation endoscopy after pulmonary vein isolation with an incidence ranging from 3% to 60%.

Active esophageal cooling during RF ablation as a means of esophageal injury prevention has been investigated through mathematical models, pre-clinical studies, and in clinical trials. Existing data support the efficacy of this approach, but the practice has not been widely adopted due to lack of a commercially available device.

A new esophageal heat transfer device (ensoETM, Attune Medical, Chicago, IL, USA) was recently commercialized for a variety of patient temperature management needs. This device provides a closed-circuit water flow through a multi-channel cylindrical silicone tube placed in the esophagus analogously to a standard orogastric tube. Warming or cooling a patient is accomplished through conductive heat transfer across the esophagus and convective heat transfer through the device.

Esophageal heat exchange is designed to take advantage of the favorable heat exchange environment created by proximity to the heart and great vessels. The device includes an independent lumen to decompress the stomach and avoid distention of the esophagus away from the device, which ensures good contact with the esophageal mucosa, thus maximizing heat transfer between the device and the patient. The esophageal heat transfer device is made of standard medical-grade silicone and is generally similar in shape and size to gastric tubes currently used and other devices routinely placed in the esophagus (esophagogastroduodenoscopy scopes, transesophageal echocardiography scopes, Ewald tubes, etc.).

Clinical studies in a variety of scenarios have shown strong support for the efficacy and safety of the esophageal heat transfer device in critical care and OR settings. Specifically, the device has demonstrated effectiveness in the intentional reduction of patient body temperature below normal for conditions such as cardiac arrest, the reduction of patient temperature from hyperthermic levels to normal range, the prevention of inadvertent perioperative hypothermia, and the reduction of elevated intracranial pressure.

A number of studies of the device have been completed, or are in progress, evaluating feasibility, safety, and effect size of esophageal protection during both RF ablation and cryoablation, including pre-clinical models and formal randomized clinical trials. Because the impact on procedural time has not yet been evaluated, the purpose of this study is to determine the impact on procedural efficiency of ablation procedures performed using esophageal heat transfer with the ensoETM.

### 3.2 Study Objective, Hypothesis and Rationale

The objective of this study is to evaluate the impact on procedural efficiency of ablation procedures performed using esophageal heat transfer to cool the esophagus during left atrial RF ablation. This study is designed to measure procedural time of RF ablation to obtain pulmonary vein isolation (PVI) and serve as a pilot to compare to historical controls and enable adequate determination of sample size requirements for a subsequent larger study. The hypothesis is that active esophageal cooling will show a reduced procedural time when compared to standard of care using esophageal temperature monitoring.

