## 4 STUDY PROTOCOL

### 4.1 Study Design

This study is a prospective, pilot study using the Attune Medical ensoETM esophageal heat transfer device to actively cool the esophagus during RF ablation procedures. This design is appropriate to gather the data needed regarding overall procedural time, compare this to historical controls, and estimate a sample size for a larger study powered for statistical significance.

Once patient consent is obtained, the subject will undergo preparation and anesthesia procedures following standard practice. Once the patient is intubated, the esophageal heat transfer device will be placed into the esophagus according to the IFU. The device will remain in place until the ablation procedure is completed and will be removed before extubation. Posterior left atrial wall ablation using standard parameters will only be performed when the ensoETM has reached a temperature of 4-6°C for at least 2 minutes. The device will be set to neutral or warming temperature (37-42°C) during other aspects of the procedure (such as mapping and anterior wall ablations).

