#### 5.4.1 Case Report Forms

The Center will perform primary data collection based on source-documented hospital chart reviews and data transcribed or exported from the mapping and navigation system. Temperature set point and timing will be transcribed and annotated into the mapping software.

Deviations from the study protocol or adverse events will be recorded on the appropriate forms (Deviation / Adverse Event Report). Deviations will be documented, and patients will be excluded from

---

final analysis although deviations will be documented and summarized in final reports. Any deviations that concern patient safety and/or the rights of a study subject will be reported to IRB within 24 hours.

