#### 5.4.3 Protocol Deviations and Modifications

Any changes to the approved clinical study must originate from Sponsor in the form of a protocol amendment that must be submitted to the relevant IRB contact. Protocol deviations should be avoided by the PI and site supporting staff. Any deviation from the protocol should be reported to the Sponsor. Any deviation to the clinical study will be reported to the ethical committee in accordance with local requirements. In the situation where deviating from the protocol is in order to protect the life or physical wellbeing of the subjects, which are considered emergency deviations, these should be reported to the Sponsor and Ethical Committee per their local guidelines.

A deviation is any variance from the Investigational Plan requirements (e.g., failure to obtain informed consent, failure to meet inclusion/ exclusion, etc.).

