#### 5.4.4 Data Analysis and Acceptance

All analyses will be performed using validated statistical software. In general, the study endpoints will be assessed relative to the study objectives. Patient data listings and tabular and graphical presentations of baseline and operative characteristics and outcome results will be created.

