##### 5.4.4.1 *Sample Size Determination*

As a pilot study, the data obtained will provide information necessary for a formal sample size estimate for a subsequent larger study. A sample size of 20 patients is estimated to be sufficient to provide a 95% confidence interval of +/- 15 minutes around mean procedure duration, assuming a procedure duration of 95 minutes with a standard deviation of 20 minutes.

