## **Evaluable Population**

All enrolled subjects who have received catheter ablation of persistent and paroxysmal atrial fibrillation with complete ablation data and procedural timing will be included in the evaluable population.

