## **Primary Endpoint Analysis**

The primary endpoint of this study will be the total time of active ablation procedure, measured from trans-septal puncture to achievement of PVI. All ablations at posterior left atrial wall during AF ablation are performed under standardized conditions including predefined sets of ablation parameters as per standard of care.

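### The historical-control comparison behind the hypothesis has no defined control set or contrast, and the deviation exclusion can act only on the cooled group

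*Combined protocol and SAP*

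**What the plan says.** Section 3.2 gives a directional, comparative hypothesis: "The hypothesis is that active esophageal cooling will show a reduced procedural time when compared to standard of care using esophageal temperature monitoring". Section 4.1 justifies the design partly because it will "compare this to historical controls, and estimate a sample size for a larger study powered for statistical significance". Table 2 lists randomization as not applicable, so historical patients are the only possible comparator.

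The analysis text is much thinner. Section 5.4.4 says: "In general, the study endpoints will be assessed relative to the study objectives". The Primary Endpoint Analysis says: "The primary endpoint of this study will be the total time of active ablation procedure, measured from trans-septal puncture to achievement of PVI"; it names no estimator, contrast or interval. The sample size in 5.4.4.1 rests on a "95% confidence interval of +/- 15 minutes around mean procedure duration", which describes one mean. The Evaluable Population is "All enrolled subjects who have received catheter ablation of persistent and paroxysmal atrial fibrillation with complete ablation data and procedural timing", so it covers enrolled patients only.

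Two further rules bear on who is analysed. Section 5.4.1 says: "Deviations will be documented, and patients will be excluded from" the final analysis. Section 5.4.3 says: "A deviation is any variance from the Investigational Plan requirements".

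**The concern.** The study is open-label and the cooled times become known as cases accrue. If the control hospital records, look-back window and selection rule are settled only afterwards, a reader cannot tell whether they were fixed without sight of the result. That affects the central question, whether cooling shortens the procedure, and is more than a gap in drafting. An effect size drawn from such a contrast could also carry over into the sizing of the larger study.

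The deviation rule adds an asymmetry. Historical patients were not treated under this protocol and cannot deviate from it, so removing deviating patients changes the cooled group and leaves the controls untouched.

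**Working it through.** **1. The plan's own figure.** Inputs from 5.4.4.1: n = 20, SD = 20 min, 95% confidence. The half-width for one mean is quantile × SD/√n:
- normal: 1.96 × 20/√20 = 8.8 min
- t with 19 df: 2.093 × 20/√20 = 9.4 min

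The stated ±15 min is not reproduced, though 20 patients are more than enough to meet it. That mismatch is a separate matter. Either way the figure concerns a single mean and not a difference.

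**2. What is fixed and what is not.**

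| Element of the comparison | Where it stands |
|---|---|
| Comparator's management | Named in 3.2 (esophageal temperature monitoring) |
| Clock | Trans-septal puncture to PVI in the Synopsis, 3.3 and Primary Endpoint Analysis; not limited to one group |
| Control source, calendar window, selection rule, number | Nowhere |
| Contrast and its interval | Nowhere |
| Rule for cases that do not reach PVI | Nowhere |

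The nearest text to a control definition is the remark in 5.2 on the Center's standards in recent years. It describes how enrolled patients are treated and does not define a control cohort.

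**3. Precision of the difference.** Assumptions: SD 20 min in both groups and all 20 cooled patients evaluable. The documents give no control number, so m = 20, 40 and 100 are shown. Half-width = t(0.975, df) × √(400/20 + 400/m), with Welch df.
- m = 20: √40 = 6.32, df 38.0, half-width 12.80 min
- m = 40: √30 = 5.48, df 38.1, half-width 11.09 min
- m = 100: √24 = 4.90, df 27.2, half-width 10.05 min

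These values give scale only. They measure sampling error and say nothing about bias from choosing controls.

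**4. Illustration of the choice itself.** Assumptions: no device effect, SD 20, 20 cooled patients, independent candidate control sets, and a nominal two-sided 5% test (the plan specifies no test). If the most favourable of k sets is picked afterwards, the simulated chance of a nominally significant result in favour of cooling is:

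| Controls per set | k = 1 | k = 2 | k = 5 | k = 10 |
|---|---|---|---|---|
| 20 | 2.5% | 4.5% | 9.1% | 14.6% |
| 60 | 2.4% | 4.0% | 6.8% | 9.5% |

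Overlapping look-back windows would inflate this less. A control period that is systematically slower behaves differently. With a 5-min shift and no device effect, the chance is Φ(5/SE − 1.96). This is 12% with 20 controls (SE 6.32) and 16% with 60 (SE 5.16), so more controls do not cure it.

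**5. Deviations.** Section 5.4.1 removes patients with deviations, and 5.4.3 makes any variance a deviation. The Evaluable Population asks only for ablation with complete ablation data and timing, and has no deviation exclusion. The two rules can give different cooled sets, and the plan does not say which one the primary analysis uses.

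**The case against.** The strongest defence is that this is a pilot. Section 4.1 reserves statistical significance for a larger study, no test or success threshold is attached to the comparison, and the cooled mean and SD needed for later sizing are obtained anyway. That stands, and it supports a hypothesis-generating label. It does not supply a method for a comparison that 3.2 and 4.1 both promise.

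Several stronger readings are tempting but not supported:
- A reader might infer that the comparator is wholly undefined. It is not: its management is named and a common clock is implied.
- A reader might infer that the sponsor means to pick controls late. The documents leave this possible and show no such intention.
- A reader might infer that the deviation exclusion favours cooling. Neither its direction nor its size can be derived from the documents.
- A reader might infer that planned precision is lost. Under the assumptions in step 3 every half-width lies inside ±15 min.
- A reader might infer that the differing exclusion wording in the Synopsis and 4.6 prevents matching. Both inclusion lists require a first left atrial ablation, and varices appear only as an example of esophageal pathology, so this mismatch is minor and separate.

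**Conclusion.** The concern holds in a limited form. A directional comparison with historical controls is a stated aim, yet the control source, window, selection rule, number and contrast are unspecified, so the control set could be settled with the cooled times in view. Separately, the deviation exclusion can act on the cooled group only and conflicts with the Evaluable Population. The plan should be changed on both counts, although the descriptive single-arm result survives without the change.

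The absence of a definition rests on the text and needs no assumption. The scale figures do: a half-width of about 12.8 to 10.05 min for the difference, against 9.4 min for one mean, assumes SD 20 in both groups, 20 evaluable cooled patients and 20 to 100 controls. The selection percentages in step 4 are illustrative and are not a forecast for this study.

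**What to change.** Make these changes before cooled times are compared with any control data, and ideally before enrolment.

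- **5.4.4.2, control set:** define consecutive first-time RF PVI patients at this centre, managed with esophageal temperature monitoring, in a stated look-back window that ends before first enrolment. Apply the same trans-septal-to-PVI clock, the same complete-timing rule and the same rule for cases that do not reach PVI.
- **Analysis set:** make the Evaluable Population, including patients with deviations, the main set for both the cooled mean and the difference, so that one cooled group serves both. Turn the 5.4.1 exclusion into a sensitivity analysis.
- **Primary Endpoint Analysis:** report the difference in mean time with a Welch 95% CI, labelled hypothesis-generating. Adjustment for AF type or operator is optional.
- **Fallback:** if control timestamps cannot be retrieved, restate 3.2 and 4.1 as a descriptive single-arm aim with no claim of reduction.

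The cost is SAP wording and a retrospective data pull, with no extra enrolment. Retrievability of historical timestamps is an assumption, since 5.4.1 describes collection for study cases. Ethics cover for past records may be needed. The interval for a difference is wider than for one mean, and keeping deviating cases may add variability.
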